9.	Evaluation of Subject(s) Capacity to Provide Informed Consent/Assent: Indicate how the personnel obtaining consent will assess the potential subject's ability and capacity to consent to the research being proposed.
qu	this study, we are not using vulnerable subjects. Subjects will be asked open-ended estions in order to evaluate their understanding of the research protocol and the risks volved.
10.	Documentation of Consent/Assent: Specify the documents that will be used during the consent/assent process. Copies of all documents should be appended to the protocol, in the same format that they will be given to subjects.
A	compound authorization and consent form will be used.
11.	Non-English Speaking Subjects: Explain provisions in place to ensure comprehension for research involving non-English speaking subjects. Translated copies of all consent materials must be submitted for approval prior to use.
N/	A
12.	Consent Waiver: In certain circumstances, the HIC may grant a full or partial waiver of consent, depending on the study. If you will request either a waiver of consent, or a waiver of signed consent for this study, complete the appropriate section below. Not Requesting a Consent Waiver Requesting a waiver of signed consent Requesting a full waiver of consent

A. Waiver of signed consent: (Verbal consent from subjects will be obtained. If PHI is collected,	
information in this section must match Section VII, Question 6)	
Requesting a waiver of signed consent for recruitment/screening only	
Requesting a waiver of signed consent for the entire study (Note that an information sheet may be	
required.)	
•	
If requesting a waiver of signed consent, please address the following:	
a. Would the signed consent form be the only record linking the subject and the research?	
∏Yes ∏No	
b. Does a breach of confidentiality constitute the principal risk to subjects?	
Yes No	
OR	
OK	
c. Does the research pose greater than minimal risk? Yes If you answered yes, stop. A waiver cannot be	•
granted. No	2
•	
AND	
d. Does the research include any activities that would require signed consent in a non-research context?	
Yes No	
B. Full waiver of consent: (No consent from subjects will be obtained.)	
Requesting a waiver of consent for recruitment/screening only	
Requesting a full waiver of consent for the study (Note: If PHI is collected, information here must	;
match Section VII, question 6.)	
If requesting a full waiver of consent, please address the following:	
a. Does the research pose greater than minimal risk to subjects? Yes If you answered yes, stop. A	
waiver cannot be granted. \(\sigma\) No	
b. Will the waiver adversely affect subjects' rights and welfare? Yes No	
c. Why would the research be impracticable to conduct without the waiver?	
d. Where appropriate, how will pertinent information be returned to, or shared with subjects at a later date?	
d. where appropriate, now will pertinent information be returned to, or shared with subjects at a rater date?	
	_
SECTION VIII: PROTECTION OF RESEARCH SUBJECTS	

Confidentiality & Security of Data:

a. What protected health information (medical information along with the HIPAA identifiers) about subjects will be collected and used for the research?

Protected health information will include all blood work, urine pregnancy in women, medical history and physical examination results.

b. How will the research data be collected, recorded and stored?

To comply with HIPAA standards, patient identification will be kept confidential. Subjects will be identified by code number, not by name during the data analysis. This data will be stored in computer files by code number, and their names will appear only on the initial form. Data that links the subject's number to the subject will be kept in password

HIC#1208010648

	SECTION IX: POTENTIAL BENEFITS
	Conservative Domestics
N/	'A
h.	Are any of the study procedures likely to yield information subject to mandatory reporting requirements? (e.g. HIV testing – reporting of communicable diseases; parent interview -incidents of child abuse, elderly abuse, etc.). Please verify to whom such instances will need to be reported.
N/	'A
g.	If appropriate, has a Certificate of Confidentiality been obtained?
Pr	inciple investigators and co-investigators only, no external agencies.
f.	Who will have access to the protected health information (such as the research sponsor, the investigator, the research staff, all research monitors, FDA, QUACS, SSC, etc.)? (please distinguish between PHI and de-identified data)
se wi	dividual's names will appear only on the initial forms and these will be kept under on a scured server. All data files that could link a code number to an individual study subject libe password protected. Once the study is completed zeroing will be used to remove my identifiable subject information.
e.	What will be done with the data when the research is completed? Are there plans to destroy the identifiable data? If yes, describe how, by whom and when identifiers will be destroyed. If no, describe how the data and/or identifiers will be secured.
	Do all portable devices contain encryption software? Yes No If no, see http://hipaa.yale.edu/guidance/policy.html
	ne documents will be password protected and held on a secured server which will only available to the principle investigator and the co-investigators.
d.	What methods and procedures will be used to safeguard the confidentiality and security of the identifiable study data and the storage media indicated above during and after the subject's participation in the study?
c.	How will the digital data be stored? CD DVD Flash Drive Portable Hard Drive Secured Server Desktop Computer Desktop Computer Other
•	otected documents and kept on a secured server. Any data that contains patient's entifying information will be released only with written consent from the patient.

Potential Benefits: Identify any benefits that may be reasonably expected to result from the research, either to the subject(s) or to society at large. (Payment of subjects is not considered a benefit in this context of the risk benefit assessment.)

Study subjects will derive no direct medical benefits from the study. However, the potential benefits of this study to society at large, and to the T1DM population in particular, are substantial in that the knowledge gained from this work should provide important information concerning the effects of recurrent, antecedent hypoglycemia on CNS responses to hypoglycemia. This information could contribute significantly to clinical indications and patient selection for the islet transplantation procedure.

SECTION X: RESEARCH ALTERNATIVES AND ECONOMIC CONSIDERATIONS

1. **Alternatives:** What other alternatives are available to the study subjects outside of the research?

No alternative treatments are available.

2. **Payments for Participation (Economic Considerations):** Describe any payments that will be made to subjects, the amount and schedule of payments, and the conditions for receiving this compensation.

Subjects assigned to Cohort 1 will receive a total of \$350 for participating in the study (\$50 for the completion of the first scan and \$300 for completion of the second scan). Subjects assigned to Cohort 2,3 and 5 will receive \$300 for completing the study. Subjects assigned to Cohort 4 will be paid \$60 for their participation. Payments will be given to the subject via a Bank of America pre-paid debit card using the Yale electronic payment service.

3. **Costs for Participation (Economic Considerations):** Clearly describe the subject's costs associated with participation in the research, and the interventions or procedures of the study that will be provided at no cost to subjects.

Subjects will not be responsible for any costs associated with the study or the screening portion prior to the study, including blood work, history and physical examination, or urine pregnancy test. We believe that given the length and number of procedures performed, the remuneration is fair and is not an excessive inducement for people to volunteer for the study.

- 4. **In Case of Injury:** This section is required for any research involving more than minimal risk.
 - a. Will medical treatment be available if research-related injury occurs?
 - b. Where and from whom may treatment be obtained?
 - c. Are there any limits to the treatment being provided?
 - d. Who will pay for this treatment?
 - e. How will the medical treatment be accessed by subjects?

If injury were to occur, we will provide any care of treatment required. Our study has no provision for additional compensation. While participating in the study procedures the overseeing physician, [name] or one of his designated co-investigators will be responsible for providing treatment. If necessary and the treatment requirement exceeds what can be provided at the study site, the participant will be transferred to the YNHH Emergency Department for further care. The participant's insurance will be billed for the

HIC#1208010648

cost of this treatment. Should problems arise after completion of the study the subjects will be provided with a telephone number to reach the PI's office and additional numbers

that will allow 24hr access to the study investigators.

TIMELINE and Blood Drawing Schedule for Hypoglycemic clamp study and recovery

Time	Real Time	YSI glucose q5 min	Insulin	Glucagon	Catachols	GCMS / other analytes	Lactate & Ketones	Cortisol and GH	Notes
A.1	Baseline	X	X	X	X		X	X	
B.1	Start insulin/ start clock	Glucose is checked every 5 minutes	X	X	X				Enter scanner
B.2	B.1 +30	X	X	X	X				
B.3	B.1 +60	X	X	X	X				
B.4	B.1 +90	X	X	X	X				
C.1 BHB Baseline	Start BHB infusion	Glucose is checked q5 min	X	X	X	X	X	X	Target glucose ~55mg/dl
C.2	C.1 +5	\downarrow				X			
C.3	C.1 +10	1				X			↓
C.4	C.1 +15	1				X			↓
C.5	C.1 +30	1	X	X	X	X	X		↓
C.6	C.1 +60	1	X	X	X	X	X	X	↓
C.7	C.1 +90	1	X	X	X	X	X		 
C.8	C.1 +120	Glucose check	X	X	X	X	X	X	End Clamp

COHORT 1:

Schedule of Events:	Screening Visit Session A	Proton-NMR Spectroscopy Session B	Carbon 13-NMR Spectroscopy Session C	Total Blood Collected
Informed Consent	X			
Medical History	X			
Physical Exam	X			
EKG	X			
Hematocrit (3 mLs)	X (3mLs)			
Creatinine (2 mLs)	X (2mLs)			
Liver Function Tests (3mLs)	X (3mLs)			
HbA1c (3mLs)	X (3mLs)			
Inclusion/Exclusion Check list	X			
Record Blood Sugar Levels 5x daily *	X			
Complete questionnaire for glucose readings <54mg/dl *	X			
Schedule two MR sessions	X			
Urine Pregnancy (females)	X	X		
IV Placement			X	
Hypoglycemic Clamp			X	
Blood Volume per visit	11 ml	none	< 250ml	< 250ml

^{*:} For diabetic subjects only

COHORT 2:

Schedule of Events:	Screening Visit	Carbon 13-NMR Spectroscopy	Total Blood Collected
Informed Consont	Session A	Session C	
Informed Consent	X		
Medical History	X		
Physical Exam	X		
EKG	X		
Hematocrit (3 mLs)	X (3mLs)		
Creatinine (2 mLs)	X (2mLs)		
Liver Function Tests (3mLs)	X (3mLs)		
HbA1c (3mLs)	X (3mLs)		
Inclusion/Exclusion Check list	X		
Record Blood Sugar Levels 5x daily *	X		
Complete questionnaire for glucose readings <54mg/dl *	X		
Schedule MR sessions	X		
Urine Pregnancy (females)	X	X	
IV Placement		X	
Hypoglycemic Clamp		X	
Blood Volume per visit	11 ml	< 250ml	< 250 ml

^{*:} For diabetic subjects only

COHORT 3:

Schedule of Events:	Screening	Proton-NMR	Total Blood
	Visit	Spectroscopy	Collected
	Session A	Session B	
Informed Consent	X		
Medical History	X		
Physical Exam	X		
EKG	X		
Hematocrit (3 mLs)	X (3mLs)		
Creatinine (2 mLs)	X (2mLs)		
Liver Function Tests (3mLs)	X (3mLs)		
HbA1c (3mLs)	X (3mLs)		
Inclusion/Exclusion Check list	X		
Record Blood Sugar Levels 5x daily *	X		
Complete questionnaire for glucose readings <54mg/dl *	X		
Schedule MR sessions	X		
Urine Pregnancy (females)	X	X	
IV Placement		X	
Hypoglycemic Clamp		X	
Blood Volume per visit	11 ml	< 250ml	< 250 ml

^{*:} For diabetic subjects only

COHORT 4:

Schedule of Events:	Screening Visit Session A	Proton-NMR Spectroscopy Session B
Informed Consent	X	
Inclusion/Exclusion Check list	X	
Urine Pregnancy	X	X
(females)		
Blood Volume per visit	none	none

COHORT 5:

Schedule of Events:	Screening Visit Session A	Cognitive Testing Session D	Total Blood Collected
Informed Consent	X		
Medical History	X		
Physical Exam	X		
EKG	X		
Hematocrit (3 mLs)	X (3mLs)		
Creatinine (2 mLs)	X (2mLs)		
Liver Function Tests (3mLs)	X (3mLs)		
HbA1c (3mLs)	X (3mLs)		
Inclusion/Exclusion Check list	X		
Record Blood Sugar Levels 5x daily *	X		
Complete questionnaire for glucose readings <54mg/dl *	X		
Schedule cognitive testing session	X		
Urine Pregnancy (females)	X	X	
IV Placement		X	
Hypoglycemic Clamp		X	
Alternate Fuel (BHB) infusion		X	
Cognitive Testing	X	X	
Blood Volume per visit	11 ml	< 250ml	< 250 ml

^{*:} For diabetic subjects only

Any unused serum collected from all cohorts may be kept for additional metabolic studies or for confirmation of findings at a future time for both subject groups (non-diabetic and diabetic).

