To define the effect of alternate fuels on brain neurotransmitter metabolism in hypoglycemia unawareness we will compare its ability to modulate the oxidation of infused stable isotope-labeled glucose in healthy adults with that in age- and weight matched subjects with c-peptide-negative T1DM with a history of hypoglycemia unawareness. During clamped hypoglycemia all subjects will undergo an NMR spectroscopy scan that permits detection of the stable isotope used, which will be either carbon13 (¹³C) or deuterium (²H). Using isotopically labeled-glucose as a tracer together with a co-infusion of 350mM unlabeled lactate, we will measure neuronal glucose metabolite enrichment, visualize them in three dimensions and determine the time courses of enrichment. These will be fitted with our metabolic model to determine whether increased lactate stimulates PDH flux and glucose oxidation under hypoglycemia and to what degree this varies across different regions of the brain.

Subject Selection and Preparation:

Two groups of subjects aged 18-65 years will be studied:

- 1) Group 1 will be T1DM subjects (C-peptide negative, HbA1c <7.5%) with a history of severe hypoglycemia and hypoglycemia unawareness as assessed by the Ryan HYPO Score (see below) and as evidenced by interview, questionnaire and glucose log and/or continuous glucose monitoring.

- 2) Group 2 will be non-diabetic healthy subjects (fasting plasma glucose < 100 mg/dL, normal HbA1c) who are matched for age and gender to the type 1 diabetic subjects, to serve as controls for the study.

The Ryan HYPO score:

During a 4-week period subjects record blood sugar levels 5 times per day. On the occasion that the glucose recorded is <54 mg/dl subjects are asked to describe the details of the event using a questionnaire recently developed at Edmonton by Ryan et al. to more objectively define hypoglycemia severity. Particular emphasis in the questionnaire is devoted to the type of symptoms and whether help was required to

reverse the hypoglycemic event. From these data a composite HYPO score is generated based on the glucose readings and the patient's reported hypoglycemic events. A composite score in the upper quartile of T1DM control patients will be required for enrollment in this study.

Subjects will be placed into one of following cohorts:

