- Cohort 1: Subjects from group 1 and group 2 will be scheduled for three study sessions as described below. A screening visit, an MR spectroscopy scan without hyperinsulinemic clamp (euglycemia) and an MR spectroscopy scan during a hyperinsulinemic clamp (hypoglycemia) with a tracer infusion.
- Cohort 2: Subjects from group 1 and group 2 will be scheduled for two study sessions. A screening visit as described below. An MR spectroscopy scan that will be conducted during a hyperinsulinemic clamp (combined eu- and hypoglycemia) together with a tracer infusion.
- Cohort 3: Subjects from group 1 and group 2 will be scheduled for two studysessions. A screening visit as described below. An MR spectroscopy scan conducted during a hyperinsulinemic clamp (combined eu- and hypoglycemia) without a tracerinfusion.
- Cohort 4: Healthy subjects from group 2 will be scheduled for one study session. They will undergo an MR spectroscopy scan without a hyperinsulinemic clamp nor any other i.v. infusions (i.e. no i.v. infusions at all).
- Cohort 5: Subjects from group 1 and group 2 will be scheduled for two studysessions. A screening visit as described below and a hyperinsulinemic clamp together with a non-labeled ketone or saline infusion without an MR spectroscopy scan.

Session A: Screening visit (YNHH Clinical Research Unit):

At the screening visit, study subjects in both the control and T1DM groups will complete the informed consent form for participation in voluntary clinical research. Demographic and clinical data collected will be reviewed by study personnel to confirm eligibility.

Once consented, all subjects will be further screened with a medical history & physical examination, blood work (electrolytes, hematocrit, creatinine, liver function tests and HbA1c) and a 12-lead electrocardiogram (EKG). Detailed subject inclusion and exclusion criteria are listed below (Human subjects – Subject recruitment). Subjects in the T1DM group only will be instructed to record their glucose readings to determine degree and frequency of hypoglycemia as described above. The subject will perform the preliminary cognitive tests at this point if they are selected for Cohort 5 at this point. The two subsequent MR sessions to complete the study will be scheduled at this point. The subject in the control group will have their two MR sessions scheduled without having to record any glucose readings.

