Session B: NMR spectroscopy without tracer infusion (Magnetic Resonance Research Center)

Subjects may be scheduled to arrive on the evening before the study if arriving early will be a difficulty. If such a case occurs, subjects will be admitted to the HRU for an overnight stay to be there for the morning without any delay.

On the morning of study, subjects will arrive directly at the MRRC. A member of the research team will verify that if the subject is from the T1DM group, the diabetic subject (as previously instructed) has taken his/her normal morning dose of insulin (or has continued to wear the insulin pump). This will not apply to subjects that are from the control group of non-diabetics participants. A urine pregnancy test will be completed on all female subjects of child bearing potential. Any female testing positive will be excluded from the study. All subjects will meet the staff, study procedures will be reviewed, and they will be exposed to the instrumentation and then placed in the scanner for NMR spectroscopy.

Imaging Procedures with the 4T/ 7T Bruker Advance NMR spectrometer (Bruker Instruments, Inc, Bellerica, MA) with a 94 cm bore: Proton MRS will be performed using the outer 1H decoupling coils of the ¹³C probe at 4T. Parameters and pulse sequences for GABA and glutamate acquisition will be the standard ones presently being established for this coil by Drs [name] and [name]: Subjects will lie supine with the occipital cortex against a 7-cm surface coil tuned to ¹H-MRS frequency of 170.4 MHz. T₁-weighted images 30 seconds in duration will be acquired for subject positioning. 1st and 2nd order shimming will be performed automatically using the FASTERMAP procedure. We will then proceed to acquiring proton NMR spectra from a volume adjacent to the NMR coil for a period of 60 minutes. Total and regional power deposition will be below the FDA safety limits for RF power deposition. For 7T studies the pulse sequence will be performed using the multi Tx coil using pulse sequences and parameters established by Dr [name], which will be verified regarding local power deposition using RF simulations. The 7T studies will be exploratory.

Session C: NMR spectroscopy with ¹³C/ ²H -tracer infusion (Magnetic Resonance Research Center)

[figure not shown]

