Non-diabetic control subjects will be asked to remain fasting from midnight prior to the study. Upon arrival to the MRRC, their blood glucose will be checked and an IV catheter will be inserted for infusion of insulin and glucose to maintain normal glucose levels and the study will ensue as described below.

For type 1 diabetic subjects receiving insulin via an insulin pump, they will be asked to check their blood glucose at home before bed and on awakening to ensure that the glucose level is above 70mg/dl and below 200mg/dl. They will be instructed to call [name] with any readings outside of this range. Upon arrival to the MRRC, their blood glucose will be checked as a safeguard, and insulin received via the insulin pump will be held. An IV catheter will be inserted for infusion of insulin and glucose to maintain normal glucose levels and the study will ensue as described below.

For type 1 diabetic subjects using multiple injections of insulin per day will be asked to ensure that the glucose level is above 70mg/dl and below 200mg/dl. As a safeguard, they

will be asked to check their blood glucose at home before bed and on awakening. Upon arrival to MRRC, their blood glucose will be checked; a nurse will place intravenous (IV) line to start infusions of glucose and insulin to maintain normal glucose levels.

At 9:00 AM on the day of this NMR session, a standard IV catheter will be inserted and used to deliver a continuous

MRS study design. After a set up period of approximately 30 minutes that includes a 1H MRS scan, subjects will be infused for 120minutes with the isotopic labeled substrate.

insulin infusion (2mU/kg/min) and a variable infusion of 20% dextrose. In addition a second IV line will be placed in the opposite arm to receive a normal saline solution and provide access for obtaining blood samples.

Once subjects arrive in the MR center they will be brought to a hypoglycemic state. The plasma glucose level will be gently lowered to 50 ± 3 mg/dL (see blood draw schedule below).

Once hypoglycemia is achieved tracer will be administered (see Figure above). Depending on the cohort assignment this will involve one of the following infusions:

 a) A 200mmol/l ¹³C /²H- alternate substrate infusion, which will be delivered through a port in the already-established IV site at a rate of 22μM/kg/min.

or

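### Cohort 3's clamp scan is scheduled as Session B, whose text is for an unclamped scan and has injection-treated T1DM subjects take their usual morning insulin

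*Combined protocol and SAP*

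**What the plan says.** The cohort list in Section V.4 describes the single scan of Cohort 3, which takes subjects from both groups and uses no tracer: "An MR spectroscopy scan conducted during a hyperinsulinemic clamp (combined eu- and hypoglycemia". The Cohort 3 Schedule of Events has two visit columns, Session A (screening) and Session B. IV placement, the row "Hypoglycemic Clamp" and a blood volume below 250 ml are marked under Session B. There is no Session C or D column.

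The Session B text in Section V.4 sends subjects from arrival to the scanner. Before that, staff check that the T1DM subject, as told beforehand, "has taken his/her normal morning dose of insulin (or has continued to wear the insulin pump". No exception is made for Cohort 3.

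The two sessions whose text does describe a clamp prepare T1DM subjects differently. In both, for pump users, "insulin received via the insulin pump will be held" on arrival. Session D also has pump users lower the basal rate by about 15% the evening before, and has injection users halve the evening long-acting dose and skip the morning injection. Session C does not say what injection users should do with their doses. Those "using multiple injections of insulin per day will be asked to ensure that the glucose level is above 70mg/dl and below 200mg/dl", and they test at home at bedtime and on waking.

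**The concern.** The Cohort 3 label leads staff to a page written for a different visit. The T1DM subjects are recruited "with a history of severe hypoglycemia and hypoglycemia unawareness as assessed by the Ryan HYPO Score", so they are the people least likely to notice a falling glucose. If the Session B instruction is applied to them, an injection user starts a hyperinsulinemic clamp with the usual morning dose already given. A pump can be stopped at the door, but an injection cannot be taken back. During the clamp the dextrose infusion can be raised to match. The exposed period is mainly afterwards, when the clamp has ended and subcutaneous insulin may still be acting. The Session B text has no recovery rule for that period.

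There is a smaller cost to the data. The Session B insulin step applies only to T1DM subjects, so any added insulin would fall in one of the two groups being compared, and Cohort 3 would be prepared differently from Cohort 5.

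**Working it through.** The plan gives no figure on this point and no calculation decides it. The check is a comparison of texts.

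**Step 1: what the label Session B covers in the Schedules of Events.**

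| Cohort | Session B column | Cohort description in Section V.4 |
|---|---|---|
| 1 | no IV, no clamp, no blood | "an MR spectroscopy scan without hyperinsulinemic clamp (euglycemia" |
| 3 | IV, clamp, less than 250 ml blood | clamp scan, no tracer |
| 4 | no IV, no clamp, no blood | healthy subjects, no infusions |

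One label therefore covers two different visits.

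**Step 2: what each session text in Section V.4 contains.**

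| Item | Session B | Session C | Session D |
|---|---|---|---|
| Site | MR center | MR center | Hospital Research Unit |
| IV, insulin and dextrose infusions | none | yes, insulin 2 mU/kg/min | yes, insulin 2 mU/kg/min |
| Glucose target | none | 50 ± 3 mg/dL | 50 ± 3 mg/dL |
| Controls | no fasting instruction | "remain fasting from midnight prior to the study" | same as Session C |
| Home glucose range 70–200 mg/dl | none | yes | yes |
| Injected insulin | normal morning dose verified | not addressed | evening long-acting halved, morning skipped |
| Pump | kept on, no hold step | held on arrival | basal cut about 15%, held on arrival |
| Recovery rule | none | 10% dextrose; above 70 mg/dL for at least 60 minutes before discharge | none |

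The Session B title excludes only a tracer. That the text was written for an unclamped scan is inferred from its content and from the Cohort 1 and 4 schedules.

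**Step 3: who is affected.**

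- Controls take no insulin. For them the gap is the missing clamp and fasting text.
- Pump users in Sessions C and D also arrive wearing the pump, which is then held. Session B lacks only that hold.
- Injection users meet an actual inconsistency: Session B expects the morning dose to have been taken, while the only explicit clamp preparation for injected insulin says to skip it.

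**Step 4: when it matters.** No insulin rate is stated for Cohort 3. Assume the 2 mU/kg/min of Sessions C and D and body weights of 50 to 100 kg:

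- 2 × 50 × 60 = 6,000 mU/h = 6 U/h
- 2 × 100 × 60 = 12,000 mU/h = 12 U/h

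The clamp itself would then deliver 6 to 12 U/h against titrated dextrose, and a subcutaneous dose would mainly raise the dextrose requirement. This does not measure the harm. It shows why the concern lies mainly after the clamp.

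**The case against.** The best defense is that nobody could run a clamp from Session B. It has no IV line, infusion rate or glucose target, so staff would have to borrow text. The nearest is Session C, which is at the same site, is also a scan, and holds the pump on arrival. This disposes of most of the pump-user issue. It does not help injection users: their dose is taken before arrival, and Session C says nothing about it.

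A reader might infer four stronger things, none of which the documents support.

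- **An unmonitored clamp.** Section V.11 requires glucose checks every five minutes with dextrose adjustment, licensed supervision, an ACLS-trained nurse with the subject throughout, and a crash cart. The appended clamp timeline repeats the five-minute checks. These control glucose during the clamp, but do not set insulin before the visit.
- **Breach of a general clamp rule.** The halve-and-skip instruction belongs to Session D, a cognitive-testing visit in another unit. It is not stated as a rule for every clamp. What is shown is inconsistent preparation.
- **A recovery gap peculiar to Session B.** The Session D text has no recovery rule either.
- **The same conflict in Session C.** Session C is silent on injected doses, which is not a contradiction, so no change is required for Cohorts 1 and 2.

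Two caveats remain. The study-group figure and the Session C figure are not visible in the text available, and they might map cohorts to sessions. The clause in Section V.4 allowing modifications concerns scheduling of scan sessions and does not cover insulin preparation.

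**Conclusion.** The point holds as an internal inconsistency. Cohort 3 is a clamp visit filed under a session text for an unclamped scan, and that text carries an insulin instruction unsuited to a clamp. The live conflict is confined to injection-treated T1DM subjects in Cohort 3, at one clamp visit each. For pump users it is an omission that can be corrected on arrival.

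No magnitude can be given. The documents state no Cohort 3 size, no split between pump and injection users, and no usual insulin dose. Harm is possible but not demonstrated. The correction should be made, because the subjects are selected for hypoglycemia unawareness and the change is small. Confidence is high on the label mismatch. It is lower on whether Cohort 3 has no preparation of its own anywhere, given the figures not seen.

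**What to change.** 1. In Session B, limit the morning-insulin and pump instruction to scans without a clamp. For T1DM subjects that means Cohort 1 only, since Cohort 4 is healthy subjects.
2. In the Cohort 3 Schedule of Events, relabel the Session B column as a tracer-free clamp session. Give it the Session C text for the clamp, control fasting, home glucose range, pump hold on arrival and recovery, without the tracer.
3. For injection users at that Cohort 3 session, apply the Session D preparation: halve the evening long-acting dose and skip the morning injection.

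The sponsor may separately wish to state what injection users should do before Session C. That is a clarification and not part of this correction.

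The cost is protocol wording, one relabeled schedule column and the matching pre-visit instruction for Cohort 3 T1DM subjects. It adds no visits, scans, blood draws or subjects, and it leaves insulin handling in Cohorts 1 and 2 unchanged.
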